The volunteers who participate in the dress rehearsal only (i.e., no ¹¹C-nicotine exposure and no PET/CT imaging) will receive a \$100 Visa gift card.

Subjects who participate in the complete study (i.e., dress rehearsal and ¹¹C-nicotine PET/CT imaging) will receive a \$250 Visa gift card, which will be provided to them after completion of all study requirements.

Version: December 20, 2017 Page **12** of **16**

By law, payments to subjects are considered taxable income.

Incidental Findings

Imaging incidental findings will not be observable in this study as the PET and CT imaging will not be of diagnostic quality.

RISKS, BENEFITS, SAFETY, AND CONFIDENTIALITY

Risks

Overall, the risk/benefit ratio of this study is minimal since the probability and magnitude of harm or discomfort anticipated in the study are not greater than what is ordinarily encountered during the performance of a routine PET/CT.

Minimal risk exists during any PET imaging. Risks are mainly due to potential impingement by the moving table and falling off the imaging table.

Radiation Risk

Dose Level A (3 mCi 11C-nicotine Dosage)

Participants will receive a e-cigarette with an total dosage of 3 mCi from the ¹¹C-nicotine, of which only a fraction will be inhaled by the participant. For the 3 mCi dosage, the PET radiotracer will yield minimal radiation exposure of 0.64 mSv.

The attenuation CT will add 0.8 mSv EDE to the overall dose exposure. For the 3 mCi ¹¹C-nicotine dosage, the combined and total EDE is 1.44 mSv. On average, a U.S. resident receives an annual radiation exposure from natural sources of about 3.6 mSv. The 1.44 mSv EDE is equivalent to 4.8 months or 146 days of natural radiation exposure. The calculated corresponding BEIR VII risk estimate may range from about one in 48,906 (0.002%) to about one in 20,469 (0.005%). This is considered minimal risk.

9 mCi ¹¹C-nicotine Dosage

If necessary, the ¹¹C-nicotine dosage may be raised to 9 mCi. Only a fraction of this dosage will be inhaled by the participant. From this dosage, participants will receive a minimal radiation exposure of 1.90 mSv.

The attenuation CT will add 0.8 mSv EDE to the overall dose exposure, so the combined and total EDE is 2.70 mSv for the 9 mCi ¹¹C-nicotine dosage. The 2.70 mSv EDE is equivalent to 9 months or 274 days of natural radiation exposure. The calculated corresponding BEIR VII risk estimate may range from about one in 11,575 (0.0086%) to about one in 4,845 (0.021%).

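### The cancer-risk range printed for the 1.44 mSv total at dose level A fits the 0.64 mSv tracer dose alone, so it appears to omit the CT and understate the risk about 2.25-fold

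*Protocol*

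**What the plan says.** The figures are all in the Protocol, under Risks, Benefits, Safety, and Confidentiality, Radiation Risk.

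- **Dose level A (3 mCi).** The tracer dose is given first: "For the 3 mCi dosage, the PET radiotracer will yield minimal radiation exposure of 0.64 mSv". The CT follows: "The attenuation CT will add 0.8 mSv EDE to the overall dose exposure". The sum is then stated: "the combined and total EDE is 1.44 mSv". This total is converted to 4.8 months, or 146 days, of natural background. The next sentence gives the cancer risk: "The calculated corresponding BEIR VII risk estimate may range from about one in 48,906 (0.002%) to about one in 20,469 (0.005"%). The sentence after that classes the risk as minimal.
- **Dose level B (9 mCi).** The structure is the same. For the tracer, "participants will receive a minimal radiation exposure of 1.90 mSv". With the same 0.8 mSv for CT, "the combined and total EDE is 2.70 mSv for the 9 mCi ¹¹C-nicotine dosage". After the background equivalent, the risk range is "about one in 11,575 (0.0086%) to about one in 4,845 (0.021"%).

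In both paragraphs the risk is described as corresponding to the dose just discussed. The dose named in the preceding sentence is the combined total, CT included.

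**The concern.** The two paragraphs apply the same kind of calculation to two total doses, so their risks should differ roughly as the doses do. They do not: the dose slightly less than doubles, while the printed risk more than quadruples. At least one of the two ranges is therefore not the risk at the dose it is attached to.

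Level A is the target dose and the one used first, so its risk statement is the one that applies to the initial participants. They are healthy volunteers with no direct benefit. The level A range comes immediately before the sentence that classes the risk as minimal, and the Protocol then compares the extra cancer risk at both levels with everyday risks. If the level A range is the wrong one, the error understates the risk. It also makes the step from A to B look like a 4.2-fold increase in risk, when the Protocol's own doses imply 1.9-fold.

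**Working it through.** **Inputs (all from the Radiation Risk section)**

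| | Level A | Level B |
|---|---|---|
| Tracer dose, mSv | 0.64 | 1.90 |
| CT dose, mSv | 0.8 | 0.8 |
| Total stated, mSv | 1.44 | 2.70 |
| Printed risk, low end | 1 in 48,906 | 1 in 11,575 |
| Printed risk, high end | 1 in 20,469 | 1 in 4,845 |

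No outside risk coefficient is used. The check assumes that risk is proportional to dose at these levels.

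**1. What reproduces.** The sums hold: 0.64 + 0.8 = 1.44 and 1.90 + 0.8 = 2.70. With the stated 3.6 mSv per year, 1.44/3.6 × 12 = 4.8 months and 1.44/3.6 × 365 = 146 days; 2.70/3.6 × 12 = 9 months and 2.70/3.6 × 365 = 273.75, printed as 274 days. The percentages agree with the one-in-N figures: 100/48,906 = 0.0020%, 100/20,469 = 0.0049%, 100/11,575 = 0.0086%, 100/4,845 = 0.0206%. Only the link from total dose to risk remains to be tested.

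**2. Ratio test.**
- Dose ratio B/A: 2.70/1.44 = 1.875.
- Risk ratio B/A: 48,906/11,575 = 4.225 at the low end; 20,469/4,845 = 4.225 at the high end.

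Curvature does not close the gap. A purely quadratic response would give 1.875² = 3.52, and matching 4.225 would need an exponent of ln 4.225 / ln 1.875 ≈ 2.29.

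**3. Same coefficients at both levels?** The width of the range is 48,906/20,469 = 2.389 for A and 11,575/4,845 = 2.389 for B. This points to one pair of coefficients applied to both levels, with only the dose entered differing.

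**4. Risk per mSv.**
- Level B at 2.70 mSv: 3.20 × 10⁻⁵ to 7.64 × 10⁻⁵.
- Level A at 1.44 mSv: 1.42 × 10⁻⁵ to 3.39 × 10⁻⁵, about 2.25 times lower.
- Level A at 0.64 mSv: 3.19 × 10⁻⁵ to 7.63 × 10⁻⁵, within 0.2% of level B at both ends.

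**5. Dose implied by level A's printed risks.** With level B's coefficient, 2.70 × 11,575/48,906 = 0.639 mSv and 2.70 × 4,845/20,469 = 0.639 mSv. Both round to the stated tracer dose. In the other direction, 0.64 mSv predicts 11,575 × 2.70/0.64 = 48,832 and 4,845 × 2.70/0.64 = 20,440, against the printed 48,906 and 20,469.

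**6. Other dose pairings.** The target ratio B/A is 4.225. The doses 2.24 and 3.50 mSv are tracer plus two CTs.

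| Level A dose | B = 1.90 | B = 2.70 | B = 3.50 |
|---|---|---|---|
| 0.64 (tracer only) | 2.97 | **4.22** | 5.47 |
| 0.8 (CT only) | 2.37 | 3.38 | 4.38 |
| 1.44 (tracer + one CT) | 1.32 | 1.88 | 2.43 |
| 2.24 (tracer + two CTs) | 0.85 | 1.21 | 1.56 |

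Only 0.64 with 2.70 fits. The next closest, 0.8 with 3.50, gives 4.375 and misses by about 3.5%.

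**7. Size of the error.**
- If level B is right, level A at 1.44 mSv should read 1 in 11,575 × 2.70/1.44 = 21,703 to 1 in 4,845 × 2.70/1.44 = 9,084, that is 0.0046% to 0.011%. The understatement is 48,906/21,703 = 2.25, which equals 1.44/0.64.
- If level A is right at 1.44 mSv, level B should read 1 in 48,906 × 1.44/2.70 = 26,083 to 1 in 20,469 × 1.44/2.70 = 10,917. Level B's printed risks would then imply 1.44 × 4.225 = 6.08 mSv, a dose that appears nowhere in the Protocol.

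**The case against.** The arithmetic is not in dispute; the objections concern cause and consequence.

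**Cause.** The Protocol gives neither its coefficients nor its calculation. That the CT was left out is inferred from a numerical match, and it presumes that level B is the correct figure. This stands as a limit on certainty. What the document itself establishes is narrower: on common coefficients, the two ranges cannot both belong to their stated totals. The match at 0.639 mSv at both ends, and the absence of another dose pairing that fits, still make CT omission much the best explanation.

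**Consequence.** After correction, level A (0.0046% to 0.011%) still lies below the disclosed level B range (0.0086% to 0.021%) at each corresponding end. It is also far below the everyday comparators the Protocol cites, such as 1 in 730. The minimal-risk sentence follows a correct total dose and a correct background equivalent as well as the risk range, so it may well survive. No endpoint, sample size or analysis uses the figure, and the move from A to B depends on image quality rather than on these risks. All of this is fair and limits the effect on the trial's results. It does not make the printed figure right. The minimal-risk sentence is also not repeated after the level B range, so the label cannot simply be assumed to carry over to a higher figure.

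**Conclusion.** The concern holds. The two printed risk ranges are inconsistent with the total doses they follow: risk rises 4.225-fold where dose rises 1.875-fold. Assuming risk proportional to dose and level B's figures as the reference, the level A range is the risk at 0.64 mSv rather than 1.44 mSv and is understated by a factor of about 2.25. The range for the stated total would be about 1 in 21,700 to 1 in 9,080. If level A were the correct pair instead, level B would be overstated by the same factor, so one pair is wrong either way. The error does not touch the trial's design or analysis, but it is a wrong participant-risk figure for the dose level used first and, on the likelier reading, errs towards reassurance. It must be corrected.

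**What to change.** Recompute both risk ranges from one stated pair of coefficients, each applied to the combined dose its paragraph names, and state those coefficients so that the result can be checked. If a tracer-only risk is wanted as well, label it as such and give it for both levels. After the correction, confirm that the minimal-risk sentence and the comparison with everyday risks still read correctly, and carry the corrected figures into any other material that uses this risk statement.

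A related point should be settled in the same edit, although this finding does not depend on it. The Measurement / Instrumentation section describes the CT as acquired both before and after the emission scan, so the Protocol should say whether 0.8 mSv covers one acquisition or both. It should also say that the risk is per imaging session, because subjects may enrol twice.

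The cost is a corrected figure that, on the likelier reading, makes level A somewhat less favourable. Conduct, sample size and analysis are unaffected.
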